#### Hypoglycemia

A participant's dose may be decreased based on hypoglycemia at any time during the study (Sections 6.5.1 and 6.5.2).

Do not increase the study intervention dose if hypoglycemia (BG  $\leq$ 70 mg/dL) is reported in the week prior to the assessment.

Although hypoglycemia criteria for dose reduction are specified in the tables for each treatment in Sections 6.5.1 and 6.5.2, it is important for the investigator to rule out any other contributing factors, such as increased physical activity or illness, which may cause an unusual occurrence of hypoglycemia. In these circumstances, the decision to reduce the dose is at the discretion of the investigator.

Study participants will be instructed to check their BG, when they experience signs and symptoms suggestive of hypoglycemia, and to administer appropriate treatment for when BG ≤70 mg/dL (3.9 mmol/L). They will be instructed to recheck BG levels 15 minutes following treatment of hypoglycemia and repeat treatment and BG recheck after another 15 minutes until the BG level has returned to the target range of 80-130 mg/dL (4.4-6.6 mmol/L) (CDC 2021). Instructions will be provided for clinical management of participants who experience frequent or repeated hypoglycemia. As necessary, additional instruction/education may be provided to participants by investigative staff, including increased BG monitoring, treatment adjustments, or other approaches (for example, behavioral interventions and lifestyle modification) to mitigate hypoglycemia frequency or severity.

#### 6.5.1. LY3209590 Dose Initiation and Adjustment

This section outlines the LY3209590

- general dosing information
- dose adjustments guidance based on FBG, and
- dose adjustment guidance based on hypoglycemia.

#### 6.5.1.1. General LY3209590 Dosing Information

#### Starting dose

The starting dose for LY3209590 occurs on Week 0 at Visit 3, and is 100 U, administered onceweekly, using a single dose autoinjector.

#### Dose escalations for Week 4 up to Week 16 (Visits 8-18)

The investigator should make every effort to follow the fixed dose escalation regimen to achieve a treat-to-target FBG of 80 to 130 mg/dL during the first 16 weeks using the fixed dose levels of 150 U, 250 U, and 400 U, administered once-weekly by single dose autoinjectors.

Assessments for potential dose adjustment will occur every 4 weeks based on a participant's median FBG and hypoglycemia events.

Participants will maintain a dose level for 4 weeks until the next assessment for potential dose increase.

#### Dose escalations after Week 16

Assessments for potential dose adjustment may occur at each visit and at least every 4 weeks.

[figure not shown]
If a participant has a fixed dose (autoinjector) escalation after Week 16, they must remain on that dose for 4 weeks before an assessment for further dose escalation.

If,	at Week 16 or after, a participant	Then
•	has been on the fixed dose of 400 U/week for at	the investigator should transition the participant to a
	least 4 weeks	variable dose delivered by the prefilled pen.
•	has a median FBG >130 mg/dL for the previous	Note: The prefilled pen provides more dosing
	week, AND	flexibility and allows dose titration above 400 U/week.
•	has not met hypoglycemia criteria described in	
	Section 6.5.1.3.	

If a participant transitions from the fixed dose autoinjector to the prefilled pen, the first dose administration with the prefilled pen will be administered at the site.

If a participant transitions from the fixed dose autoinjector to a prefilled pen, they must continue using the prefilled pen for the remainder of the study.

#### LY3209590 dose escalation schema

Abbreviations: AI = autoinjector; FBG = fasting blood glucose; U = units.

Details for dose reduction in response to hypoglycemia are given in Section 6.5.1.3.

<sup>1At 4 weeks, 8 weeks, 12 weeks, 16 weeks, and per visit schedule thereafter.

<sup>2Participant must remain on the autoinjector dose for 4 weeks before next assessment for dose escalation.

 $^{3}80-130 \text{ mg/dL}.$ 

<sup>4Participants who transition to the prefilled pen must continue to use this device for the remainder of the study.

## 6.5.1.2. LY3209590 Dose Adjustments Based on Fasting Blood Glucose

## Dose adjustments for participants on a fixed dose administered by the autoinjector

Assessments for potential dose adjustment will occur every 4 weeks.

This table provides guidance for dose adjustments if the participant is on a fixed dose administered by a single dose autoinjector.

If the median	FBG is	And	Then
<80 mg/dL	<4.4 mmol/L	the participant has not met hypoglycemia criteria described in Section 6.5.1.3	
 
do not change the dose.
 
make recommendations to the participant to reduce hypoglycemia risk or occurrence, for example 
 
o more frequent BG monitoring
 
o consider behavioral interventions and lifestyle modifications.
 
 
 

80-130 mg/dL (target) >130 mg/dL	4.4-7.2 mmol/L >7.3 mmol/L		do not change the dose.  increase the LY3209590 dose to the next higher single dose autoinjector dose level.
>130 mg/dL at or after Week 16	>7.3 mmol/L at or after Week 16	the participant  • has been on a fixed dose of 400 U/week for at least 4 weeks, and  • has not met hypoglycemia criteria described in Section 6.5.1.3.	the investigator should transition the participant to a prefilled pen with variable dose capabilities above 400 U/week.

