### Participants randomly assigned to receive LY3209590

Participants randomly assigned to receive LY3209590 will be on a fixed dose escalation for at least the first 16 weeks of the study. Participants will start LY3209590 on a fixed dose of 100 U per week and will escalate the LY3209590 doses every 4 weeks to the set doses of 150, 250, and 400 U per week, as required, until an FBG of 80 to 130 mg/dL is achieved in the preceding week. A fixed-dose autoinjector will be used to administer each dose.

Treat-to-target dose adjustments will be based on FBG and hypoglycemia events.

After Week 16, if a participant who has received the fixed dose of 400 U per week for at least 4 weeks has median FBG levels >130 mg/dL, then the investigator should transition the participant to titratable doses using a prefilled pen. This will provide more dosing flexibility and allow dose titrations above 400 U per week.

If a participant transitions from the fixed-dose autoinjector to a prefilled pen, they must continue using the prefilled pen for the remainder of the study.

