#### Weeks 16-52 (Visits 18-33)

Participants assigned to LY3209590 will remain on their fixed dose according to the dosing instructions in Section 6.5.1.

During Weeks 16-52, if a participant is receiving the fixed dose of 400 U/week for at least 4 weeks and they have a median FBG >130 mg/dL for the previous week, the investigator should transition the participant to a prefilled pen, which will provide more dosing flexibility for higher doses. See Section 6.5.1 for details.

If a participant changes from the autoinjector to the prefilled pen, they will complete additional procedures per the SoA at the time of change and administer the first dose at the site.

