#### General insulin dose adjustment considerations

### Fasting blood glucose

Dosing will be individualized based on FBG and hypoglycemia events.

The FBG treat-to-target is 80 to 130 mg/dL (4.4 to 7.2 mmol/L), inclusive.

Use the median FBG for dose adjustment and follow this guidance:

- Determine the median FBG from the 3 most recently recorded FBG readings from the 7-day period prior to the site visit.
- If only 2 FBG measurements are available, use the lower of the readings for the dose assessment.
- If only 1 FBG measurement is available, the investigator determines if a dose change is necessary.

Investigators are expected to follow the dosing regimen for the protocol. However, modifications of the basal insulin dose may be influenced by other clinical circumstances or safety considerations known to the investigator. If the investigator prescribes a dose other than the regimen recommended dose, the investigator is responsible for documenting the clinical rationale for the prescribed dose.

When considering any dose adjustments (in either treatment group), the investigator will also review whether the participant experienced any documented episodes of hypoglycemia. If the participant experienced any documented BG  $\leq$ 70 mg/dL ( $\leq$ 3.9 mmol/L) in the previous week, the basal insulin dose should not be increased.

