## 6.5.2.2. Insulin Glargine Dose Adjustments According to Fasting Blood Glucose

This table provides guidance for dose adjustments based on median FBG recorded during the previous week.

If the median FBG is		Then
<80 mg/dL	<4.4 mmol/L	reduce the dose by 3 U.
80-130 mg/dL (target)	4.4-7.2 mmol/L	do not change the dose.
131-140 mg/dL	7.3-7.7 mmol/L	increase the dose by 3 U.
>140 mg/dL	>7.7 mmol/L	increase the dose by 6 U.

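### The autoinjector dosing table pairs >130 mg/dL with >7.3 mmol/L; 130 mg/dL is 7.2 mmol/L, so a median of 7.3 mmol/L falls between rows

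*Protocol*

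**What the plan says.** Protocol 6.5 (Fasting blood glucose) sets the target at "80 to 130 mg/dL (4.4 to 7.2 mmol/L), inclusive". The synopsis has LY3209590 escalated "until an FBG of 80 to 130 mg/dL is achieved in the preceding week". The pen-switch rule is given in mg/dL only, in Section 4.1 ("they have a median FBG >130 mg/dL for the previous week") and again in Section 6.5.1.1 ("has a median FBG >130 mg/dL for the previous" week).

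The autoinjector table in Section 6.5.1.2 prints both units. Its mg/dL column is continuous: no change from 80 to 130, then an increase above 130. In the mmol/L column the same two rows read "4.4-7.2 mmol/L >7.3 mmol/L". The pen-switch row repeats the figure: ">7.3 mmol/L at or after Week 16".

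The prefilled-pen table in the same section and the glargine table in Section 6.5.2.2 pair 131-140 mg/dL with 7.3-7.7 mmol/L. In both, 7.3 mmol/L calls for a higher dose.

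**The concern.** A trigger above 7.3 mmol/L is not the same rule as a trigger above 130 mg/dL. If the no-change row ends at 7.2 and the increase row starts above 7.3, a median of exactly 7.3 has no instruction in that column.

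This is a decision threshold in the titration scheme that the trial is testing. A site working in mmol/L could leave an autoinjector participant at the current level, although the same median would add 3 U per day for a glargine participant. Through Week 16 planned LY3209590 assessments are four weeks apart (Section 6.5.1.1) and glargine is assessed weekly (Section 6.5.2.1), so a missed LY3209590 step lasts longer.

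There is also a small reporting consequence. SAP Appendix 2 counts prescribed doses that differ from the algorithm's recommendation. At 7.3 mmol/L the two columns of the table disagree on what that recommendation is.

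**Working it through.** **Conversion factor.** Two pairs in the protocol imply it: 54 mg/dL with 3.0 mmol/L (Section 8.3.6) and 270 mg/dL with 15 mmol/L (Section 6.1.2). 54/3.0 = 18.0 and 270/15 = 18.0. Factors from 18.0 to 18.0182 were tried, and the conclusion is the same for all of them.

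**The plan's own figure.** 130/18 = 7.22, shown as 7.2. This reproduces the target limit in Section 6.5 but not the 7.3 in the autoinjector table.

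**What the printed trigger means.** 7.3 × 18 = 131.4 mg/dL (131.5 with 18.0182). The mmol/L cell therefore sets the trigger about 1.5 mg/dL above the 130 printed beside it.

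**Which readings fall in the gap.** Under Section 6.5 the dosing value is the median of three readings, or the lower of two, so it is always an actual reading.

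| mg/dL | ÷ 18 | shown as (mmol/L) | mg/dL column | mmol/L column |
|---|---|---|---|---|
| 130 | 7.222 | 7.2 | no change | no change |
| 131 | 7.278 | 7.3 | increase or switch | no row |
| 132 | 7.333 | 7.3 | increase or switch | no row |
| 133 | 7.389 | 7.4 | increase or switch | increase or switch |

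At one decimal, 7.3 mmol/L covers 7.25 × 18 = 130.5 to 7.35 × 18 = 132.3 mg/dL, that is, whole-number readings of 131 and 132.

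**After correction.** With >7.2 mmol/L in both cells, 7.3 falls in the increase and switch rows. The column has no gap and agrees with the 7.3 lower bound in the pen and glargine tables.

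**A related rounding case.** 140/18 = 7.778, shown as 7.8. In mg/dL, 140 belongs to the 131-140 row. In mmol/L, 7.8 falls in the top row, above 7.7. For glargine the mmol/L column would then say "increase the dose by 6 U" instead of 3 U, and for the pen 40 U instead of 20 U. This concerns one whole-number reading.

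**A separate editorial slip.** The recheck instruction in Section 6.5 (Hypoglycemia) gives "80-130 mg/dL (4.4-6.6 mmol/L". But 6.6 × 18 = 118.8 mg/dL, so the upper figure should be 7.2. It has no effect on titration.

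**The case against.** The strongest reply is that the rule is not missing. The right mg/dL trigger stands in the same row, Sections 4.1 and 6.5.1.1 and the synopsis state the rules in mg/dL alone, and Section 6.5 ends the target at 7.2 mmol/L inclusive. An investigator with a median of 7.3 would find the answer in the next cell. The table is offered as guidance, to be used with clinical judgment. The worst likely outcome is that a participant 1 or 2 mg/dL above target waits until the next assessment. Nothing in the documents shows that any site titrated in mmol/L.

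All of this stands, and it limits the effect. It does not make the entry right: no reading of the protocol supports 7.3 as the equivalent of 130 mg/dL.

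One could also suppose that a greater-than-or-equal sign was intended, which would make both cells correct. The plain greater-than sign appears in both, however, while ≥ is printed in the hypoglycemia tables of Sections 6.5.1.3 and 6.5.2.3. Even if ≥ was intended, the printed cells need correcting.

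Finally, SAP Version 3 was approved late, before database lock, so a correction may come too late to change any dosing. That affects the use of the fix, not the error.

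**Conclusion.** The concern holds, as a minor error. Two cells of the autoinjector table give a mmol/L threshold that is 0.1 too high, and a median of 7.3 mmol/L (131 or 132 mg/dL) is left without a row. The gap exists only for LY3209590 participants on the autoinjector, and only where a site reads the mmol/L column alone.

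This rests on the conversion factor implied by the protocol and on glucose being shown to one decimal in mmol/L. The frequency cannot be estimated, because neither the meter's display unit nor the glucose distribution is given. Use of mmol/L is plausible, since the dosing tables print both units and the SAP plans US and non-US subgroups. Sample size, power and the primary analysis are unaffected.

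**What to change.** - In the autoinjector table of Protocol 6.5.1.2, change both >7.3 mmol/L entries to >7.2 mmol/L (equivalently ≥7.3 at one decimal).
- Add one sentence to Section 6.5: where rounded mmol/L values differ from the mg/dL thresholds, mg/dL governs. This also settles 140 mg/dL in the pen and glargine tables.
- As a separate editorial correction, change 4.4-6.6 to 4.4-7.2 mmol/L in the recheck instruction of Section 6.5 (Hypoglycemia).

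The cost is two table entries, one sentence, one editorial correction and a short memo to sites. Sample size, visits and analyses do not change. If dosing has finished, state in SAP Appendix 2 that the mg/dL threshold defines the recommended dose for the compliance summary, and correct the table before it is reused.

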#### Dose adjustment for participants on a variable dose administered by a prefilled pen

If a participant transitions from the single dose autoinjector to a prefilled pen, they must continue using the prefilled pen for the remainder of the study.

Assessments for potential dose adjustment may occur weekly or at least every 4 weeks.

This table provides guidance for dose adjustments if the participant is transitioning to or using the prefilled pen.

If the median FBG is		Then
<80 mg/dL	<4.4 mmol/L	reduce the LY3209590 dose by 20 U.
80-130 mg/dL (target)	4.4-7.2 mmol/L	do not change the dose.
131-140 mg/dL	7.3-7.7 mmol/L	increase the LY3209590 dose by 20 U.
>140 mg/dL	>7.7 mmol/L	increase the LY3209590 dose by 40 U.

## 6.5.1.3. LY3209590 Dose Adjustments Based on Hypoglycemia Events

#### Guidance for participants receiving 100 U LY3209590

If a participant is receiving a 100 U LY3209590 dose and experiences hypoglycemia, the investigator will

- rule out any other contributing factors, such as increased physical activity or illness, which may cause an unusual occurrence of hypoglycemia, and
- discontinue intervention if participant meets dose reduction criteria due to hypoglycemia.

#### General guidance

If a participant experiences any hypoglycemia event (BG  $\leq$ 70 mg/dL) in the previous week and their FBG is >130 mg/dL at the next dose assessment time point, the investigator should not increase the dose. In this situation, the only time the investigator should increase the dose is if they determine that it was an unusual occurrence of hypoglycemia that was explained by other contributing factors, such as increased physical activity or illness.

#### Dose adjustments for participants on a fixed dose administered by the autoinjector

This table provides guidance for dose adjustments based on hypoglycemia events.

If a participant using the autoinjector reports	With a blood glucose value of	Then
≥3 hypoglycemic events	≤70 mg/dL (3.9 mmol/L)	
≥1 hypoglycemic event	<54 mg/dL (3.0 mmol/L)	
≥1 nocturnal hypoglycemic event	≤70 mg/dL (3.9 mmol/L)	reduce the LY3209590 dose to the
any confirmed severe hypoglycemia		next lower autoinjector dose level.
(neurological impairment confirmed		
by investigator)		

If the autoinjector dose is reduced due to hypoglycemia, the participant should remain on the lower dose for the remainder of the study, unless a further dose decrease is required due to hypoglycemia.

#### Dose adjustment for participants on a variable dose administered by a prefilled pen

This table provides guidance for dose adjustments based on hypoglycemia events.

If a participant using a prefilled	with a blood glucose value of	then
pen reports		
≥3 hypoglycemic events	≤70 mg/dL (3.9 mmol/L)	
≥1 hypoglycemic event	<54 mg/dL (3.0 mmol/L)	
≥1 nocturnal hypoglycemic event	≤70 mg/dL (3.9 mmol/L)	
Any confirmed severe		reduce the LY3209590 dose by 40 U.
hypoglycemia		
(neurological impairment confirmed		
by investigator)		

#### 6.5.2. Insulin Glargine Dose Initiation and Adjustment

This section outlines the insulin glargine

- general dosing information
- · dose adjustment guidance based on FBG, and
- dose adjustment guidance based on hypoglycemia.

#### 6.5.2.1. General Insulin Glargine Dosing Information

All insulin glargine doses will be administered using a prefilled pen.

The starting dose for insulin glargine occurs on Week 0 at Visit 3.

The starting dose for insulin glargine is 10 U/day.

The investigator will use an individualized flexible dose approach throughout the study with weekly assessments for potential dose adjustment during the 52 weeks of treatment.

## 6.5.2.2. Insulin Glargine Dose Adjustments According to Fasting Blood Glucose

This table provides guidance for dose adjustments based on median FBG recorded during the previous week.

If the median FBG is		Then
<80 mg/dL	<4.4 mmol/L	reduce the dose by 3 U.
80-130 mg/dL (target)	4.4-7.2 mmol/L	do not change the dose.
131-140 mg/dL	7.3-7.7 mmol/L	increase the dose by 3 U.
>140 mg/dL	>7.7 mmol/L	increase the dose by 6 U.

## 6.5.2.3. Insulin Glargine Dose Adjustments According to Hypoglycemia Events

A participant's dose may be decreased based on hypoglycemia at any time during the study.

#### Dose adjustments for participants receiving insulin glargine

This table provides guidance for dose adjustments based on hypoglycemia events.

If a participant reports	With a blood glucose value	Then
	of	
≥3 hypoglycemic events	≤70 mg/dL (3.9 mmol/L)	reduce the dose by 2 to 6 U.
≥1 hypoglycemic event	<54 mg/dL (3.0 mmol/L)	
≥1 nocturnal hypoglycemic event	≤70 mg/dL (3.9 mmol/L)	Dose reductions of 2 or 4 U may
any confirmed severe hypoglycemia (neurological impairment confirmed by investigator)	_	occur every 3 days to achieve a weekly 6 U reduction as clinically indicated.

## 6.6. Continued Access to Study Intervention after the End of the Study

The sponsor will not provide participants with any ongoing supplies of study intervention after they have completed the study treatment period or permanently discontinued the study intervention.

## **6.7.** Treatment of Overdose

An overdose of LY3209590 or insulin glargine, defined as a dangerously large amount of insulin compared to the protocol-prescribed dose, will be reported as per Section 10.3.1. In the event of an overdose, refer to the IB for LY3209590 or product label for insulin glargine depending on the participant treatment assignment.

In the event of an overdose, the investigator or treating physician should:

- contact the medical monitor immediately
- consider holding non-insulin diabetes medications, if clinically appropriate
- evaluate the participant to determine, in consultation with the medical monitor, whether study intervention should be interrupted or whether the dose should be reduced
- closely monitor the participant for any AE or SAE and laboratory abnormality until study intervention no longer has a clinical effect, and
- obtain a plasma sample for PK analysis if the participant is assigned to LY3209590.

## **6.8.** Concomitant Therapy

#### Concomitant therapy regimens

All participants should maintain their usual medication regimens for concomitant conditions or diseases throughout the study, unless those medications are specifically excluded in the protocol (see Section 5.2).

Participants taking concomitant medications should be on stable dosages at the time of screening and should remain at stable dosages throughout the study, unless changes need to be made because of an AE or rescue therapy (see Section 6.1.2).

Acceptable non-insulin diabetes treatments are described in Section 6.8.3.

#### **Changing concomitant therapy**

Participants should consult with authorized study personnel before taking any new medications during the study, except when initiated for treatment of medical emergencies. Authorized study personnel should consult the sponsor's medical monitor if there are any questions about concomitant therapies during the study.

#### Concomitant therapy data collection

For therapy that the participant is receiving at the time of enrollment or receives during the study, including over-the-counter medications, authorized study personnel should collect

- the name of medication, vaccine, or therapy
- the reason for use, and
- dates of administration, including start and end dates.

For diabetes and lipid-modifying medications, collect dosage information including dose and frequency.

Nonstudy medications taken by study participants who have signed informed consent, but are not randomly assigned, will not be reported unless an SAE or AE occurs that the investigator believes may have been caused by a study procedure.

## 6.8.1. Medications with Approved Weight Loss Indication

#### Allowed usage of weight loss medication during the study

A participant may use a medication that promotes weight loss if they are on stable therapy 90 days prior to screening.

Allowed medications include, but are not limited to

- over-the-counter medications, including food supplements that promote weight loss
- liraglutide 3.0 mg
- orlistat
- sibutramine
- mazindol
- phentermine
- lorcaserin
- phentermine and topiramate combination
- naltrexone or bupropion, or
- semaglutide injection 2.4 mg.

## Prohibited usage of weight loss medication during the study

After screening, no prescription or over-the-counter medications that promote weight loss may be initiated or changes in dosage allowed.

